3.7 Steps that will be taken to control or mitigate the risks

The risks associated with MRI scanning of subjects implanted with implantable active medical devices have been identified through clinical evaluation, including an exhaustive literature search.

Risks normally associated with ICDs and transvenous leads will be minimized in the study by selecting investigators who are experienced in treating subjects implanted with ICDs,

Clinical Investigational Plan

evaluating implanted ICD systems, and who are trained in the MRI Ready IDE Study. Subjects will be actively monitored during the study scan using verbal communication, ECG, and continuous pulse oximetry monitoring. The investigator or other ACLS-certified personnel who have been trained on the study protocol will be present during the study MRI scan to address cases of asystole or hemodynamic collapse that may occur during the study MRI scan. In addition, because the study MRI scan is not meant to be diagnostic in nature, contrast agents will not be used, thereby eliminating the risk of allergic or adverse reactions to contrast agents.

Risks will also be minimized by careful assessment of each subject prior to enrollment. After enrollment, subjects in the study will be followed as specified in this CIP to monitor the condition of the implanted system and the battery after the subject has undergone the study MRI scan.

In order to safely perform an MRI scan on a subject with the implanted study system, the physician/clinician should do the following as stated in the MRI Procedure Information for the St. Jude Medical® MR Conditional pacing system:

- Confirm that the patient has an MR Conditional System
- Confirm that no adverse conditions to MRI scanning are present (e.g. additional hardware)
- Review the potential adverse events
- Generate a report of the patient's permanently programmed parameters
- Select and Save MRI Settings
- Review the MRI Checklist and Program the MRI Settings using the Merlin® PCS
- Subject receives the MRI Scan
- Disable MRI Settings Using the Merlin® PCS

After the MRI scan and at the 1 Month Post Scan visit, the ICD will be interrogated to verify appropriate ICD function, to evaluate pacing and sensing characteristics, and to assess any adverse events.

Overall, the clinical study design, subject selection process, and procedures developed for scanning and monitoring of the subject during the MRI scan have all been designed to minimize risks to the subject.

While steps have been taken to identify and reduce or minimize risks associated with the study MRI scan and participation in the study, there may be risks that are unknown at this time due to the investigational nature of this study.

Clinical Investigational Plan

3.8 Risk-to-benefit rationale

There may be no direct clinical benefit to the subject for participating in this study; no direct therapy is being provided as part of the study procedures, i.e. the study MRI scan. However, these data will help to establish the safety and efficacy of the Durata or Optisure lead and the Ellipse VR ICD in an MRI environment, which, upon approval, will provide patients who need an ICD to have the option to be safely scanned should these patients need to undergo an MRI in the future.

4.0 Study Design

4.1 Purpose

The intent of this IDE study is to evaluate the safety and efficacy of the Durata or Optisure lead and Ellipse VR ICD that have undergone an MRI scan. The patient population under study includes patients indicated for or who have been implanted with a Durata or Optisure lead and an Ellipse VR ICD.

4.2 Study Design and Scope

The study intends to enroll patients, including Medicare beneficiaries, who have been implanted with a Durata or Optisure lead and Ellipse VR ICD to evaluate the effects of an MRI scan on the aforementioned devices. The evaluation will be performed as part of a regulated, prospective, multi-center, non-randomized, single-arm clinical trial. This design was chosen for generalizability of study results by enrolling subjects across multiple geographies and varying types of sites, with the minimum sample size required to demonstrate the safety and efficacy of the Durata or Optisure lead and the Ellipse ICD in an MRI environment.

Subjects that agree to participate in the MRI Ready IDE study will also be approached to enroll in a sub study of the MRI Ready IDE study which will involve induction testing that is performed post MRI visit.

Ventricular tachycardia (VT) and ventricular fibrillation (VF) events will also be collected to characterize ventricular arrhythmia sensing and detection post-MRI. A minimum of 25 device detected VT/VF events (induced or spontaneous) will be collected post MRI from a minimum of 25 subjects with at least one ventricular arrhythmia episode (spontaneous or induced) adjudicated by the Ventricular Arrhythmia Events Committee through any one of three methods:

1. Events obtained during induction testing at any time after the MRI visit, including system revision and follow up visits where induction testing was performed due to impaired R-wave sensing or other clinical reasons.

Clinical Investigational Plan

2. Events in subjects who enroll in the sub study, which will involve post MRI induction testing
3. Subjects who are not enrolled in the sub study will be followed via Merlin.net or phone call every 3 months post baseline visit to collect potential spontaneous VT/VF episodes after the MRI visit. The data collection effort will end upon notification from SJM.

Data collected to demonstrate safety of the Durata or Optisure lead and the Ellipse VR ICD include MRI scan related complications and deaths resulting from the study MRI scan. Data collected to demonstrate efficacy of the study devices include changes in the device's capture and sensing thresholds from the pre-MRI scan testing to 1-Month post MRI testing.

4.2.1 Number of Subjects Required to be Included in the Study

The maximum number of subjects in the study is 165. A maximum of 41 (25% of the total, if the total subjects enrolled = 165) subject enrollments will be allowed per center.

A patient will be considered enrolled in the main study after he/she signs the main study consent, meets all of the inclusion and none of the exclusion criteria verified during the pre-MRI testing, and the MRI Settings have been programmed.

4.2.2 Estimated Time Needed to Enroll Subject Population

Enrollment in this clinical study is expected to take approximately 12 months. The anticipated duration of this study is 1.5 to 2 years, depending on the rate of enrollment and regulatory timelines.

The minimum duration of each subject's participation, if he/she undergoes an MRI scan, in the study is 23 days. All subjects will have the Durata or Optisure lead implanted for at least 60 days prior to enrollment.

The following study visits will occur after enrollment:

- MRI scan/Post Scan testing
- 1 Month Post Scan visit

The MRI Scan should take place no sooner than 60 days post lead implant or lead revision procedure where the Durata or Optisure lead was implanted or repositioned. The 1 Month Post Scan visit is based on the MRI Scan Visit.

Clinical Investigational Plan

A data collection effort to collect VT/VF events will also take place. For subjects on Merlin.net, the Merlin.net records will be reviewed for spontaneous VT/ VF events. Subjects not on Merlin.net will be contacted by phone and their medical records will be screened every 3 months for VT/VF events since the last visit. The data collection effort will end upon notification from SJM.

4.3 Objectives

4.3.1 Primary Objectives

The primary objectives of this study are to assess the safety and efficacy of the Durata or Optisure lead and Ellipse VR ICD in an MRI environment.

4.4 Endpoints

4.4.1 Primary Safety Endpoint

Safety for the Ellipse VR ICD involving the Durata and Optisure leads will be evaluated in terms of:

- Freedom from MRI scan-related complications for the Ellipse VR ICD involving Durata or Optisure (RV) lead from MRI scan to 1 month post-MRI scan testing is greater than 90%

4.4.2 Primary Efficacy Endpoints

Efficacy of the Durata and Optisure leads involving the Ellipse VR ICD will be evaluated in terms of:

- Proportion of Durata or Optisure (RV) leads implanted with the Ellipse VR ICD with capture threshold increase of $\leq 0.5V$ at 0.5ms from pre-MRI scan to 1 month post-MRI scan testing is greater than 90%
- Proportion of Durata or Optisure (RV) leads implanted with the Ellipse VR ICD with sensing amplitude decrease of $\leq 50\%$ from pre-MRI scan testing to 1 month post-MRI scan is greater than 87%

4.4.3 Additional Data

The following data will also be collected.

- Demographics: gender, age, ethnicity, race, cardiac disease history, arrhythmia history, indication for ICD implant, history of smoking, etc.
- Device electrical measurements at the MRI Scan Visit (before and after the scan) and at the 1 Month Post Scan Visit
- ADE, SADE, UADE/USADE
- Mortality

Clinical Investigational Plan

- Number of non-study related MRI scans
- Proportion of VT/VF episodes with significant detection delay assessed from device-detected VT/VF episodes (induced or spontaneous) with stored electrogram available
- Summarize number of subjects that returned to usual programming after the MRI scan and number of subjects, if any, experiencing delays in reprogramming

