System Revision (if applicable)		Can occur any time after baseline	
 Interrogate device Obtain applicable in-clinic lead measurements: bipolar capture¹, sense², pacing and HVLI impedances for cases where the lead was repositioned, or was replaced with another Durata/ Optisure lead, or where the ICD was replaced with another Ellipse ICD. NOTE: If the device replacement/revision of the Ellipse VR device occurs post MRI visit and the Durata/Optisure lead remains in its original location, then induction testing may occur and the session records related to induction testing should be uploaded. Evaluate subject for ADE, SADE, and UADE (for US sites) or USADE (for OUS sites) events and submit an AE CRF (as applicable). Report deviations, death, withdrawal and out of service as applicable Upload device session records through the EDC study site portal

Clinical Investigational Plan

Study Visit	Visit Window	Study Procedures and Data Collection
Unscheduled (if applicable)	Any time after the MRI scan visit (where the subject is seen in clinic due to an ADE, SADE or UADE associated with the Durata or Optisure or Ellipse ICD or for follow up related to the collection of VT/VF episodes)	
 Interrogate device. Obtain applicable in-clinic Durata or Optisure lead measurements: bipolar capture, sense, pacing and HVLI impedances^{1,2} If an unscheduled visit occurs prior to the 1 month post MRI visit, evaluate subject for ADE, SADE, and UADE (for US sites) or USADE (for OUS sites) events and submit an AE CRF (as applicable). If an unscheduled event occurs after the 1 month post MRI visit, then the AE events do not need to be submitted. If a subject experiences reduced R waves and undergoes induction testing or undergoes induction testing for another clinical reason after the MRI visit, then an induction testing form will be submitted. Report deviations, death, withdrawal and out of service as applicable Upload device session records through the EDC study site portal

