
 • Lead electrode heating and tissue damage resulting in loss of sensing or capture or both • Lead heating resulting in thrombus formation or embolism • Device heating resulting in tissue damage in the implant pocket or subject discomfort or both • Induced currents on leads resulting in continuous capture, VT/VF, hemodynamic collapse, or all three • Damage to the device or leads causing: 
 a. the system to fail to detect or treat irregular heartbeats b. the system to treat the subject’s condition incorrectly • Damage to the functionality or mechanical integrity of the device resulting in the inability of the device to communicate with the programmer • Movement or vibration of the device or leads • Lead dislodgment • Competitive pacing and potential for VT/VF induction due to ambulatory asynchronous pacing in MRI mode • Pulmonary Embolism 	
These risks are mitigated through the selection of investigators who are qualified by training and/or experience to evaluate and treat subjects implanted with an ICD system.
 
In addition, study investigators will be trained on the study protocol to ensure the proper procedures are followed to assure subject safety during the study MRI scan. This includes continuous monitoring of the subject using pulse oximetry, ECG and verbal communication during the scan.
 
Advanced Cardiac Life Support (ACLS) procedures will be in place to address situations where a life threatening arrhythmia and/or hemodynamic collapse occurs. The programmer will be used outside the American College of Radiology (ACR) defined Zone 4 magnet room. If the subject’s hemodynamic function is compromised during the MRI scan, the MRI scan will be stopped, and proper measures will be taken to restore the subject’s hemodynamic function.

Potential ICD Related Events	

 • Refer to the Ellipse user’s manual for a full list of potential adverse events 	
The Ellipse VR ICD is a market-released ICD. The adverse events associated with this ICD are the same as those associated with other market-released ICDs.
 
These risks are mitigated through the

Clinical Investigational Plan

Event	Mitigation
	selection of investigators who are qualified by training and/or experience to evaluate and treat subjects implanted with an ICD.
Potential Lead Related Events	

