Unscheduled (if applicable)		Any time after the MRI scan visit (where the subject is seen in clinic due to an ADE, SADE or UADE associated with the Durata or Optisure or Ellipse ICD or for follow up related to the collection of VT/VF episodes)	
 Interrogate device. Obtain applicable in-clinic Durata or Optisure lead measurements: bipolar capture, sense, and pacing and HVLI impedances, ^{1,2} if possible If an unscheduled visit occurs prior to the 1 month post MRI visit, evaluate ADE, SADE, UADE (for US sites) or USADE (for OUS sites) events and submit an AE CRF (as applicable). If an unscheduled event occurs after the 1 month post MRI visit, then the AE events do not need to be submitted. If a subject experiences reduced R waves and undergoes induction testing or undergoes induction testing for another clinical reason after the MRI visit, then an induction testing form will be submitted. 	
 Follow Up CRF AE CRF If applicable: 
 Deviation CRF Death CRF Screening Failure/Withdrawal CRF Product Out of Service CRF Induction Testing CRF

Clinical Investigational Plan

Study Visit	Visit Window	Study Procedures and Data Collection	Forms and CRFs
		
 Report deviations, death, withdrawal and out of service, as applicable Upload device session records through the EDC study site portal 	

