8.1.2 Adverse Device Effect (ADE)

An adverse device effect is an adverse event related to the use of an investigational medical device.

This definition includes adverse events resulting from insufficient or inadequate instructions for use, deployment, implantation, installation, or operation, or any malfunction of the investigational medical device.

This definition includes any event resulting from the use, error, or from intentional misuse of the investigational medical device.

Clinical Investigational Plan

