14.0 Study Committee

14.1 Clinical Events Committee (CEC)/Ventricular Arrhythmia Event Review Committee (VAC)

The CEC is responsible for providing an independent review and adjudication of CIP pre-defined clinical events. The CEC will consist of at least 3 members. The CEC will be comprised of independent and unblinded physicians that are not investigators, DSMB members or steering committee members in the trial. St. Jude Medical will appoint members of the CEC and the chairperson. St. Jude Medical may facilitate the CEC meeting, but will not be voting members.

Reportable events to be collected under this protocol will be adverse device effects outlined in sections 8.1.2-8.1.6. The CEC will base their final adjudication on the information provided on the case report forms, medical records, and their clinical knowledge and experience. The CEC will also review and classify all subject deaths under this protocol. The primary function, responsibilities and membership of the CEC will be described in detail in a CEC charter .

The Ventricular Arrhythmia Event Review Committee (VAC) will review all device detected VT and VF episodes with a stored electrogram available and non-sustained VT/VF episodes of at least 16 beats. The members of the CEC will also be members on the VAC.

VT/VF episodes with at least 4 intervals ≥ 300 ms, with 1 interval ≥ 600 ms, or with the pre-detection time lasting more than 10 seconds, will be evaluated by the VAC for ventricular arrhythmia undersensing and amount of detection delay. A clinically significant detection delay is defined as ≥ 5 seconds.

Clinical Investigational Plan

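### The post-MRI detection-delay proportion admits only episodes the device detected, so a sustained induced VT/VF that is never detected drops out of it

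*Combined protocol and SAP*

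**What the plan says.** Section 4.4.3 of the protocol lists, among the additional data, "Proportion of VT/VF episodes with significant detection delay assessed from device-detected VT/VF episodes (induced or spontaneous) with stored electrogram available". Section 4.2 gives the purpose: VT/VF "events will also be collected to characterize ventricular arrhythmia sensing and detection post-MRI". It also sets the collection target in terms of device-detected events, at least 25 from at least 25 subjects. Table 2 in section 3.3 names, among the consequences of damage to the device or leads, "the system to fail to detect or treat irregular heartbeats".

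Section 14.1 sets up an arrhythmia review committee, called the VAC, which "will review all device detected VT and VF episodes with a stored electrogram available and non-sustained VT/VF episodes of at least 16 beats". Episodes meeting certain interval or pre-detection-time criteria "will be evaluated by the VAC for ventricular arrhythmia undersensing and amount of detection delay", and a delay of 5 seconds or more is clinically significant.

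Other records exist. Sections 6.6.1.1 and 6.6.1.2 require upload of session records after induction tests and an AE form as applicable, and Table 5 lists an Induction Testing CRF. Section 8.1.2 brings within the adverse device effect (ADE) definition "or any malfunction of the investigational medical device".

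On AE reporting, the unscheduled-visit row of Table 1 (Synopsis) states: "If an unscheduled event occurs after the 1 month post MRI visit, then the AE events do not need to be submitted". The same row of Table 5 (section 6.2) repeats that "then the AE events do not need to be submitted".

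**The concern.** A delay summary conditioned on detection leaves out the extreme case, in which detection never comes. For spontaneous episodes little can be done, because an arrhythmia the device missed is not reliably known. For inductions it is different: the arrhythmia is provoked deliberately, with staff present and a form to complete, so a miss can be ascertained.

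The three primary endpoints concern complications, capture threshold and sensing amplitude. This proportion is therefore the only listed summary built specifically on VT/VF detection. Having 25 subjects with an adjudicated episode is also a condition for the dataset freeze (section 12.2.5) and for the marketing submission (Synopsis). A reader may take a low delay proportion as evidence that detection is intact after MRI. As defined, it shows only that detection was prompt when it happened.

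**Working it through.** **No plan figure to reproduce.** Section 4.4.3 gives no expected rate, interval or threshold for this item, and the minimum of 25 is stated without derivation. The check is to follow one hypothetical episode, a sustained induced VF never detected by the scanned system, through the text.

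1. *Section 4.4.3.* It is not device-detected, so it is outside both numerator and denominator.
2. *Section 4.2.* The target of 25 events is also counted in device-detected events, so on that wording the episode does not count and collection continues to the next detected one.
3. *Section 14.1, first limb.* It fails for the same reason.
4. *Section 14.1, second limb.* It qualifies only if it is non-sustained and lasts 16 beats or more. Section 14.1 does not define non-sustained. The only definition of sustained in the protocol is in section 6.5.2.1 (above 150 bpm for more than 30 seconds), written for monitoring during the scan. If borrowed here, an undetected VF ended within 30 seconds would reach the VAC and a longer one would not. Either way, VAC review does not bring it into the 4.4.3 proportion.
5. *Section 14.1, time criterion.* A pre-detection time above 10 seconds presupposes that detection occurred.
6. *Session record, Induction Testing CRF, ADE report.* Each may capture the episode. None feeds the proportion.

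**Illustration of size (all counts assumed).** Let d be detected episodes, x those delayed by 5 seconds or more, and k undetected inductions, with one episode per subject.

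- Plan: x/d.
- Delayed or not detected: (x + k)/(d + k).
- Exact two-sided 95% upper limit for y events in n: the 97.5% quantile of Beta(y + 1, n − y). For y = 0 this is 1 − 0.025^(1/n); with n = 25 it gives 13.7%.

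With x = 0:

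| d | k | Plan (upper limit) | Delayed or not detected (upper limit) |
|---|---|---|---|
| 25 | 0 | 0/25 (13.7%) | 0/25 (13.7%) |
| 25 | 1 | 0/25 (13.7%) | 1/26 = 3.8% (19.6%) |
| 25 | 2 | 0/25 (13.7%) | 2/27 = 7.4% (24.3%) |
| 25 | 3 | 0/25 (13.7%) | 3/28 = 10.7% (28.2%) |

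The plan column does not move with k. The 25 may include spontaneous episodes, so the induced line could be shorter:

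| d (induced) | k | Plan (upper limit) | Delayed or not detected (upper limit) |
|---|---|---|---|
| 20 | 1 | 0/20 (16.8%) | 1/21 = 4.8% (23.8%) |
| 15 | 1 | 0/15 (21.8%) | 1/16 = 6.3% (30.2%) |
| 10 | 1 | 0/10 (30.8%) | 1/11 = 9.1% (41.3%) |

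**Mixed systems.** Section 6.8.2 encourages induction on a new Ellipse generator at a revision after the scan. With the lead left in place, that tests a scanned lead with an unscanned generator. Section 6.8 requires a System Revision CRF for generator replacement, so these episodes can be identified, but the protocol does not say they are reported separately.

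**AE reporting.** For an induction done for clinical reasons at an unscheduled visit after the 1-month visit, Tables 1 and 5 say AE events need not be submitted, while section 6.6.1.2 asks for an AE form as applicable. The same table rows cover induction for reduced R waves, so the two instructions meet on the same visit.

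**The case against.** The strongest reply is that delay and non-detection are different outcomes. A delay cannot be timed without detection, and non-detection has its own route: it is an anticipated event, malfunction is an ADE, section 8.2.2 makes ADEs reportable, and section 14.1 puts the members of the Clinical Events Committee, which adjudicates ADEs, on the VAC too. This stands as far as it goes. A reader might infer that undetected inductions would go unrecorded, or that the VAC could never see them. The documents support neither reading, given these routes, the CRF and session records, and the undefined term in section 14.1. But an ADE listing has no denominator of inductions and does not correct the proportion.

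Three cautions about remedies also stand. Counting every induction that produced any VT/VF would score brief self-terminating runs, or VT below the programmed rate, as device failures. Section 6.6.1.1 does not limit sub-study subjects to one induction, so an exact binomial interval on episodes would ignore clustering. And an undetected episode may leave no stored electrogram to adjudicate.

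Finally, every count above is assumed, and the SAP (section 12.0), the committee charter (section 14.1) and the CRFs (Appendix K) are separate documents not available here. Any of them may already classify undetected inductions.

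**Conclusion.** The point holds, as a minor one. On the protocol's wording, a sustained induced VT/VF that is never detected cannot enter the detection-delay proportion, and section 14.1 does not clearly send it to the VAC. If such an episode occurs, the figure is too favourable for its stated purpose. In the illustration, one to three such episodes beside 25 detected ones move the result from 0% to between 3.8% and 10.7%. This assumes one episode per subject and no delays among detected episodes. If none occurs, the figure is unaffected.

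A reader might infer that the trial's conclusion is at risk, or that detection performance will in fact be overstated. The documents do not support that: the item is descriptive, section 12.3 rests success on the three primary endpoints alone, and no non-detection rate is given. The conflict over AE submission is real but is a separate matter of reconciliation.

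**What to change.** Check the SAP, charter and CRFs first. If they are silent, amend sections 4.4.3 and 14.1 and the charter:

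1. For post-MRI inductions, take as denominator those that produced sustained VT/VF meeting the programmed detection criteria, and define sustained for this purpose.
2. Report *not detected* as its own category and within a combined *delayed or not detected* proportion. If an exact interval is given, compute it by subject or on one episode per subject.
3. Have the VAC review undetected cases from the session record, the Induction Testing CRF and whatever tracing already exists.
4. Keep spontaneous device-detected episodes on a separate line.
5. Flag episodes recorded on a generator implanted after the study scan, using the System Revision CRF.

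Separately, reconcile the unscheduled-visit rows of Tables 1 and 5 with section 6.6.1.2 on AE submission after the 1-month visit.

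The cost is wording, a few table rows and, if the Induction Testing CRF does not record non-detection, one added field. No subjects, visits or tests are added. The downsides are that the reported figure may be less favourable and that some undetected cases may be hard to adjudicate from existing records.
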